8.3.2 Bone Turnover Markers

Missing bone turnover maker (either baseline or post-baseline values) will not be imputed. Any values below the lower limit of quantification (LLOQ) will be imputed using the LLOQ for analysis.

8.3.3 Dates

No imputation will be done on incomplete stop date of an AE or a concomitant medication. The imputation rules for incomplete start dates of AEs or concomitant medications are provided in [Table 8-1](#) and [Table 8-2](#). AEs with a partially missing start date that occur prior to Study Day 1 will be considered pre-treatment AEs and excluded from safety analyses.

Table 8-1. Imputation Rules on Partial Start Date of AE or Concomitant Medication

	Missing	Impute	Exception
Start Date	Day	01	Default to Study Day 1 Date if the event started in the same year and month as Day 1
	Day / Month	01JAN	Default to Study Day 1 Date if the event started in the same year as Study Day 1
	Month	JAN	Default to Study Day 1 if the event started in the same year as Study Day 1
	Day / Month / Year	First Dose Date	Use randomization date for subjects who did not receive investigational product

Table 8-2. Imputation Rules on Partial Start Date of IP Administration in AI/Pen Arm

	Missing		Impute
Start Date	Day		Dispensed date (If the month and year of start date is the same with the month and year of dispensed date) 01 (If the month of start date is different with month of dispensed date)
	Day / Month		Dispensed date
	Month	If the year is the same with the year of dispensed date	Month of dispensed date (if the day is larger or equal to the day of dispensed date) Month of dispensed date plus one (if the day is less than the day of dispensed date)
		If the year is different with the year of dispensed date	Month of dispensed date plus one

If a death date is incomplete and missing only the day field, it will be imputed as the first day of the month if the latest date from other data is before the month of the death. However, if the latest date is during the same month as the death, the partial death date will be imputed using the latest date.

For dates of last menstrual period, the imputation rules for partial dates are as follows: if the day is missing, default to day 15; if both month and day are missing, default to July 1st. If the imputed date is on or after the randomization date, default to randomization date minus 1. Missing years will not be imputed under any conditions.

8.3.4 Laboratory Parameters

Laboratory parameters with values below the LLOQ or above the upper limit of quantification (ULOQ) will be imputed as the LLOQ or ULOQ value, respectively.

8.4 Detection of Bias

Not Applicable.

8.5 Outliers

Observations found to be due to data entry errors will be corrected by the study team before final database lock. Potential outliers that are not due to data entry error will be included in the primary analysis. The validity of any questionable values will be confirmed. No valid measurement will be purposely excluded from descriptive or inferential analyses. However, sensitivity analyses may be conducted to evaluate the influence of extreme values in the data. These analyses will be documented in the clinical study report.

8.6 Distributional Characteristics

The assumptions underlying the parametric models analyzed for continuous data will be checked. In cases where residuals indicate marked departures from the assumptions, additional sensitivity analyses will be performed using transformations or alternate methods such as nonparametric or robust procedures.

8.7 Validation of Statistical Analyses

Programs will be developed and maintained and output will be verified in accordance with current risk-based quality control procedures.

Tables, figures, and listings will be produced with validated standard macro programs where standard macros can produce the specified outputs.

The production environment for statistical analyses consists of Amgen-supported versions of statistical analysis software; for example, the SAS System version 9.4 or later.

9. Statistical Methods of Analysis

9.1 General Considerations

For computation of change from baseline endpoints, baseline will be taken as the observation recorded just prior to first dose of IP. In the case in which the protocol specifies multiple baseline measurements to be taken, the mean of the baseline records will be used for analysis.

Continuous variables will be summarized descriptively using mean, median, standard deviation, 25th percentile, 75th percentile, minimum, maximum, and the number of non-missing observations. Frequencies and percentages will be presented for nominal categorical variables.

9.2 Subject Accountability

The disposition of all randomized subjects will be tabulated by randomized treatment group. Subject enrollment and disposition for the number (%) of subjects randomized, successfully completing investigational product administration, completing the 6-month treatment period (Primary Analysis), and completing the study (Final Analysis) will be included. The disposition of subjects will also include the number (%) of subjects who withdrew from the IP and their reasons for withdrawal.

9.3 Important Protocol Deviations

Important Protocol Deviations (IPDs) categories are defined by the study team before the first subject's initial visit and updated during the IPD reviews throughout the study prior to database lock. These definitions of IPD categories, subcategory codes, and descriptions will be used during the course of the study. Eligibility deviations are defined in the protocol.

9.4 Demographic and Baseline Characteristics

Subject demographic and baseline disease characteristics as listed below will be summarized by treatment group based on the Full Analysis Set defined in [Section 6.1](#).

- Race
- Ethnicity (Hispanic, non-Hispanic)
- Age at randomization
- Age groups (< 65, ≥ 65 years; < 75, ≥ 75 years; ≥ 18 - < 65 years, ≥ 65 - < 75 years, ≥ 75 - < 85 years, ≥ 85 years)

- Body composition (height [cm], weight [kg], BMI [kg/m²])
- BMD T-score at the lumbar spine, total hip and femoral neck
- Bone turnover markers (sCTX, P1NP)
- Years since menopause
- Fracture history (Yes, No)
- Laboratory parameters (calcium corrected by albumin, phosphorus, creatinine, serum 25(OH) vitamin D, eGFR)
- Prior osteoporosis medication use (Yes, No)
- Substance use, including tobacco use (never, former, current)
- Baseline use of vitamin D (Yes, No)
- Baseline use of calcium (Yes, No)
- Parental fracture (Yes, No, Unknown)

9.5 Efficacy Analyses

The baseline value of BMD and machine type will be included in the statistical model for primary and secondary efficacy analyses. For each of the efficacy BMD endpoints (lumbar spine, total hip, and femoral neck at Month 6), descriptive statistics will be provided for absolute values at baseline by machine type. Additionally, absolute values, change from baseline, and percent change from baseline at Month 6 will be provided by machine type.

9.5.1 Analyses of Primary Efficacy Endpoint

The primary analysis to assess the percent change from baseline in DXA BMD at lumbar spine at Month 6 will employ an analysis of covariance (ANCOVA) model using observed data. The ANCOVA model will include randomized treatment, baseline value of BMD, machine type, and interaction of baseline BMD value and machine type as prognostic variables. Summaries for the results will include least-squares means point estimates of the percent change from baseline for each treatment arm. The model will allow for heterogeneity between treatments. The 2-sided 95% CI and associated p-value will be provided for the difference between the least-squares means for HCP-administered 210 mg romosozumab by PFS and self-administered 210 mg romosozumab by AI/Pen.

Conclusions for the primary efficacy hypothesis of efficacy of self-administration of romosozumab by AI/Pen compared with HCP-administered romosozumab by PFS at lumbar spine BMD at Month 6 will be made using a 1-sided test with type 1 error rate of 0.025 and noninferiority margin of -2.0%. The primary efficacy analysis set will be used

In addition, summaries of treatment-emergent adverse events occurring in at least 5% of the subjects and serious adverse events occurring in at least 0.1% of the subjects by preferred term in any treatment arm will be provided in descending order of frequency.

Summaries of treatment-emergent and serious adverse events will be tabulated by system organ class, preferred term, and grade.

Subject incidence of disease-related events will be summarized for all treatment-emergent disease-related events and fatal disease-related events by system organ class and preferred term.

The subject incidence of treatment-emergent adverse device effects will also be summarized.

9.6.1.1 Events of Interest

Subject incidence of events of interest (EOI; standardized MedDRA queries and/or Amgen customized queries) will also be summarized according to their categories and preferred term. Events of interest of hypersensitivity and malignancy will be identified using a narrow search/scope in standardized MedDRA queries (SMQ). Event of interest of hypocalcemia, injection site reaction, and osteoarthritis will be identified using Amgen-defined MedDRA search strategies. Adjudicated-positive adverse events of atypical femoral fracture (AFF), osteonecrosis of the jaw (ONJ), and serious cardiovascular adverse events will also be summarized as EOIs as described in [Sections 9.6.1.1.2, 9.6.1.1.3, and 9.6.1.1.4](#), respectively.

9.6.1.1.1 Injection Site Reaction

The duration, severity and nature (concomitant, recurrent) of the injection site reactions will be summarized. The time (in days) to first injection site reaction will also be summarized descriptively.

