An adverse device effect is any adverse event related to the use of a combination product or medical device. Adverse device effects include adverse events resulting from insufficient or inadequate instructions for use, adverse events resulting from any malfunction of the device, or adverse events resulting from use error or from intentional misuse of the device.

Recording Adverse Events, Disease-related Events (if applicable), and Serious Adverse Events

Adverse Event, Disease-related Event (if applicable) and Serious Adverse Event Recording

- When an adverse event, disease-related event or serious adverse event occurs, it is the responsibility of the investigator to review all documentation (eg, hospital progress notes, laboratory, and diagnostics reports) related to the event.
- The investigator will then record all relevant adverse event/disease-related event/serious adverse event information in the Event CRF.
 - Additionally, the investigator is required to report a fatal disease-related event on the Event CRF.
- The investigator must assign the following adverse event attributes:
 - Adverse event diagnosis or syndrome(s), if known (if not known, signs or symptoms);
 - Dates of onset and resolution (if resolved);
 - Severity (or toxicity defined below);
 - Assessment of relatedness to investigational product, other protocol-required therapies, or devices; and
 - Action taken.
- If the severity of an adverse event worsens from the date of onset to the date of resolution, record a single event for each increased level of severity on the Event CRF.
- It is not acceptable for the investigator to send photocopies of the subject's medical records to the sponsor in lieu of completion of the Event CRF page.
- If specifically requested, the investigator may need to provide additional follow-up information, such as discharge summaries, medical records, or extracts from the medical records. In this case, all subject identifiers, with the exception of the subject number, will be blinded on the copies of the medical records before submission to the sponsor.
- The investigator will attempt to establish a diagnosis of the event based on signs, symptoms, and/or other clinical information. In such cases, the diagnosis (not the individual signs/symptoms) will be documented as the adverse event/serious adverse event.

Evaluating Adverse Events and Serious Adverse Events

Assessment of Severity

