5.6 Arithmetic Calculations

Percent Change from Baseline

The change from baseline value divided by the baseline value and multiplied by 100:
$$((\text{value at date of interest} - \text{baseline value}) / \text{baseline value}) * 100.$$

Subject Incidence for AEs

The subject incidence for a given event in a given time period is defined as the number of subjects with at least 1 reported occurrence of the event divided by the number of subjects who are at risk for having the event at the beginning of the given time period. For subjects with multiple occurrences of the same event, the event will only be counted once per subject.

6. Analysis Sets

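### A partly dated injection-site reaction can be dated before the injection that caused it, and the SAP does not say whether duration and recurrence are computed on CRF records or on whole reactions

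*SAP*

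**What the plan says.** SAP 9.6.1.1.1 plans two things for injection-site reactions: "The duration, severity and nature (concomitant, recurrent) of the injection site reactions will be summarized"; and "The time (in days) to first injection site reaction will also be summarized descriptively". It does not define duration, concomitant or recurrent. It also does not say whether the unit is a CRF record or a clinical reaction.

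Two other rules determine the data behind these summaries.

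- **Recording.** Protocol Appendix 4 (the part on recording adverse events) tells the investigator, when an event worsens, to "record a single event for each increased level of severity on the Event CRF". Each event carries its own onset and resolution dates. The text does not say whether the second record starts at the original onset or at the worsening.
- **Partial dates.** SAP 8.3.3, Table 8-1, sets a missing start day to 01. The exception is "Default to Study Day 1 Date if the event started in the same year and month as Day 1". For end dates, "No imputation will be done on incomplete stop date of an AE or a concomitant medication". Table 8-2 treats AI/Pen dose dates differently: a missing dose day is set to the dispensing date when the month and year agree.

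For incidence, SAP 5.6 states: "For subjects with multiple occurrences of the same event, the event will only be counted once per subject". SAP 7.2 and 7.3 make all safety analyses descriptive, without testing.

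**The concern.** Injection-site reactions follow injections. A rule that puts onset on the 1st of the month without looking at the dose date can place the reaction before its cause. That distorts time to first reaction and duration, both of which use the onset date. The contrast with Table 8-2 shows the gap. If an AI/Pen dose and its reaction both lack the day in the same month, outside the Day 1 month, the SAP puts the dose on the dispensing date and the reaction on the 1st. Whenever dispensing was after the 1st, that order is impossible for a reaction to that dose.

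The severity-splitting rule raises a second question. A reaction that goes from mild to moderate without a break becomes two records. With no joining step, each is shorter than the reaction, and the second may be read as a recurrence.

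At stake is the description of an event of interest that has its own SAP subsection, in a trial that compares two ways of injecting the same drug.

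**Working it through.** The plan gives no figure on this point to reproduce. The check is date arithmetic. Study Day comes from SAP 5.2 (date minus Day 1, plus 1). Duration is taken as stop minus start plus 1, which is an assumption because the SAP defines none. All calendar dates below are assumed for illustration.

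**1. Size of the shift from a missing start day.** A true onset on day d of the month is moved to day 1, so the shift is d − 1. With onsets spread evenly over a month of L days, the mean shift is (L − 1)/2 and the maximum is L − 1.

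| Days in month | Mean shift | Maximum shift |
|---|---|---|
| 28 | 13.5 | 27 |
| 30 | 14.5 | 29 |
| 31 | 15.0 | 30 |

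**2. One reaction.** Day 1 is 10 March, the second dose is 10 April (Study Day 32), true onset is 11 April, worsening is on 13 April and the end is 16 April.

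| | Onset used | Study Day of onset | Duration (days) |
|---|---|---|---|
| True dates | 11 April | 33 | 6 |
| Start day missing, Table 8-1 | 1 April | 23 | 16 |
| Start day missing, dose date used | 10 April | 32 | 7 |

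Under Table 8-1 the onset falls 9 days before the dose (32 − 23).

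**3. Day 1 month.** A true onset on 12 March with the day missing becomes 10 March, so Study Day 1 instead of 3. The exception keeps the imputed onset from falling before the first dose.

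**4. Effect on the mean time to first reaction.** Only first reactions with a missing start day outside the Day 1 month are moved. The share f is not in the documents. With a mean shift of 14.5 days, the mean moves earlier by f × 14.5: about 0.15 days at 1%, 0.7 at 5% and 1.5 at 10% (assumed shares).

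**5. Splitting, same reaction with complete dates.** If the second record starts on the worsening date, the records run 11–13 April (3 days) and 13–16 April (4 days), with a mean of 3.5. If the first record ends the day before, they last 2 and 4 days, with a mean of 3. The reaction lasted 6 days. In general, if a share w of reactions worsens once and the pieces share no day, the mean record duration is D/(1 + w), where D is the mean reaction duration. For assumed w of 10%, 20% and 30% the factors are 1/1.1 = 0.91, 1/1.2 = 0.83 and 1/1.3 = 0.77, so 9%, 17% and 23% too short.

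**6. What splitting leaves alone.** The earliest record keeps the original onset, so time to first is Study Day 33 with or without splitting. Subject incidence counts a subject once per event. The primary analysis uses lumbar spine BMD only.

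**7. Direction.** Imputation lengthens duration (6 to 16 days in the example) and splitting shortens it (6 to 3.5 or 3). The net error in mean duration has no fixed sign.

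**The case against.** The strongest reply is that the splitting problem is hypothetical. SAP 9.6.1.1.1 names no unit of analysis, so nothing says that each record counts as a reaction or that back-to-back records count as recurrence. An experienced programmer might join them. Missing start days may also be rare: onset date is a required event attribute in Appendix 4, and adverse events are collected at every monthly treatment visit. Both rules apply equally to both arms, the summaries are descriptive, and the device-specific safety endpoint named in the objectives is adverse device effects.

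Most of this stands and limits the size of the point. It does not remove it. Table 8-1 is a stated rule, not a gap, and it produces the early onset whenever the start day of a reaction to a later dose is missing and that dose was given after the 1st of the month. On splitting, the silence itself is the problem, because the result depends on an unstated choice in an open-label trial. Part of SAP 9.6.1 is not readable in the available text, but the replacement wording for that section in the SAP amendment description has no joining rule.

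Three objections to a simple remedy also stand. Each dose is two injections, given into different sites, so joining all overlapping records with the same term would merge separate reactions and erase the concomitant category. Using the dose date without a check can put onset after resolution, for example when a reaction to a late dose in the previous month ended before this month's dose. AI/Pen dose dates may themselves be imputed under Table 8-2, so reliance on them could bring in a difference between arms.

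**Conclusion.** The point holds as a minor one. For partly dated reactions to later doses, Table 8-1 can date onset before the dose, making time to first reaction too early and duration too long by up to 30 days per affected record. The frequency is not given. For worsening reactions, duration is understated and recurrence can be overstated only if records are analysed as entered, which the SAP neither requires nor rules out. The percentages for splitting and the shifts in the mean rest on assumed shares.

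A reader might infer more than the documents support:

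- That the summaries will be wrong. This depends on missing start days or on unjoined records, and neither is established.
- That splitting changes time to first reaction. It cannot.
- That duration is understated overall. Imputation acts in the opposite direction.
- That reactions will be reported against the wrong dose. No visible planned output summarizes reactions by dose or dosing interval.
- That one arm is disadvantaged. Incomplete dates may be more common after unsupervised home doses, but the documents give no rates.
- That incidence or the noninferiority conclusion is at risk. Neither is affected.

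**What to change.** **SAP 8.3.3.** For an injection-site reaction with a missing start day, impute the recorded dose date in that month when there is exactly one and it is not after the stop date. Otherwise keep the Table 8-1 rule. Flag every record with an imputed onset, and show duration and time to first reaction with and without those records.

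**SAP 9.6.1.1.1.** State that the unit is the reaction. Join only records of the same reaction that continue one another at a higher grade, and take the first onset, last resolution and maximum grade. Keep separate simultaneous reactions apart and count them as concomitant. Count a reaction as recurrent only after a reaction-free gap, and state how long that gap must be. Define duration, for example as stop minus start plus 1. Where records cannot be linked with confidence, leave them unjoined.

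**Cost.** SAP wording and a short extra derivation on data already collected. The remaining weakness is reliance on AI/Pen dose dates that may be imputed under Table 8-2; presenting results without imputed onsets shows whether this matters. Using the dose date also assumes onset on the day of injection, an error of one day in the example above against ten days under the current rule.

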9.6.1.1.2 Atypical Femoral Fracture

The events of AFF which occurred on study will be adjudicated and summarized. All potential events of AFF identified through a pre-defined search of the MedDRA terms will be submitted to the AFF Adjudication Committee for review and adjudication. The committee will determine whether the event meets the case definition criteria for AFF.

9.6.1.1.3 Osteonecrosis of the Jaw

The events of ONJ which occurred on study will be adjudicated and summarized. All potential events of ONJ identified through a pre-defined search of the MedDRA terms

will be submitted to the ONJ Adjudication Committee for review and adjudication. The committee will determine whether the event meets the case definition criteria for ONJ.

9.6.1.1.4 Adjudicated-positive Serious Cardiovascular Adverse Events

The following baseline cardiovascular risk factors will be summarized descriptively:

- Age and age groups (<75 and ≥ 75 years)
- Smoking history (Current/former, never, unknown)
- History of cardiovascular-related medical history
 - History of hypercholesterolemia (Yes, No)
 - History of hypertension (Yes, No)
 - History of diabetes (Yes, No)
 - History of cardiovascular disease (Yes, No)
 - History of central nervous system vascular disorder (Yes, No)
- Narrowly-defined history of cardiovascular disease:
 - History of ischemic heart disease (Yes, No)
 - History of coronary artery disease (Yes, No)
- History of cerebrovascular disease/event, atrial fibrillation, or atrial flutter:
 - History of central nervous system haemorrhages and cerebrovascular conditions (Yes, No)
 - History of cerebrovascular disease (Yes, No)
 - History of ischemic stroke or TIA (Yes, No)
 - History of atrial fibrillation/atrial flutter (Yes, No)
- History of cardiovascular or cerebrovascular event:
 - History of stroke, myocardial infarction or revascularization (Yes, No)
 - History of stroke or myocardial infarction (Yes, No)
 - History of stroke (Yes, No)
 - History of myocardial infarction (Yes, No)
 - History of revascularization (Yes, No)
 - History of heart failure (Yes, No)

Cardiovascular medical history risk identification strategy is defined in [Appendix C](#).

All deaths and potential cardiovascular-related serious adverse events will be submitted to an external independent committee comprised of experienced cardiologists for adjudication. The committee will adjudicate the events and determine whether the event is cardiovascular in nature.

Only events confirmed positive by the adjudication committee to meet cardiovascular event definition criteria will be included for analysis. Adjudicated-positive serious

cardiovascular events of death, cardiac ischemic event, cerebrovascular event, non-coronary revascularization, heart failure and peripheral vascular events not requiring revascularization will be summarized using subject incidence rates. No statistical tests will be performed.

